3.2 Discussion of study design

The intention of this NIS is to collect data on the persistence and adherence to anticoagulant therapy of AF patients with dabigatran etexilate or VKA in daily practice.

An NIS appears the most suitable instrument for obtaining information about the use of medicines in everyday therapeutic practice and thus for investigating prospectively unresolved questions in everyday therapeutic practice as independently as possible.

A sample of 4000 patients offers the opportunity to document and assess the persistence and adherence to anticoagulant therapy of AF patients during therapy with dabigatran etexilate or VKA in a representative patient population.

3.3 Choice of patient population

The treatment decision is made independently of participation in this NIS and is taken before participation is considered.

A list of patients who have given their consent to participate in the NIS will be kept for each site. This list will be stored confidentially in the study folder.

3.3.1 Main diagnosis

Four thousand patients with non-valvular atrial fibrillation, in whom anticoagulant treatment with Pradaxa® or VKA is indicated in accordance with the guidelines and in line with the Summary of Product Characteristics, must be observed in about 1000 practices (community-based cardiologists and primary care internists / general practitioners) in this NIS.

Before the start of therapy with Pradaxa® or VKA, due note must be taken of the contraindications. See also the respective current Summaries of Product Characteristics of Pradaxa® or the VKA used.

Patients treated with VKA must also theoretically be treatable with dabigatran etexilate to ensure comparability of the patient populations.

3.3.2 Inclusion criteria:

Patients can be included if all the following criteria are present:

- Newly prescribed treatment with Pradaxa® (dabigatran etexilate)/VKA in the indication "Stroke prevention in non-valvular atrial fibrillation" (AF) respecting the indication and contraindications as described in the respective Summary of Product

Characteristics Pradaxa® 110 mg or 150 mg hard capsules or the appropriate VKA (patients are eligible for both Pradaxa® and VKA therapy).

- Only patients who are eligible *both* for therapy with Pradaxa® *and* for therapy with VKA in accordance with the respective Summaries of Product Characteristics are documented (patients eligible for VKA *and* Pradaxa®)
- Treatment with dabigatran etexilate or VKA is given in accordance with the respective Summaries of Product Characteristics. The routine diagnostic procedures and treatment that would be undertaken irrespective of the study are unaffected.
- Only patients on VKA therapy who would also be eligible for therapy with dabigatran etexilate in accordance with the Pradaxa® Summary of Product Characteristics are documented.
- Patients must have signed the patient consent form before inclusion in the NIS.

3.3.3 *Exclusion criteria*

- Patients with the general and special contraindications mentioned in the packaging leaflet or Summary of Product Characteristics must not be included.

The Summaries of Product Characteristics for Pradaxa® are contained in the NIS study folder in the register "Summaries of Product Characteristics".

For the selected VKA, the observing physician must use the current Summary of Product Characteristics of the product concerned for guidance.

- Patients participating at the same time or within the last 30 days in another NIS or an interventional clinical trial must not be included.
- Patients treated with anticoagulants for a condition other than non-valvular atrial fibrillation must not be included.
- Pradaxa® and VKA should not be used during pregnancy and lactation. Pregnant or breastfeeding women must therefore not be included in the NIS.

3.3.4 *Exclusion of patients from the NIS*

3.3.4.1 *Exclusion of individual patients from the NIS*

The individual patient has the right to withdraw their consent to participate in the NIS at any time. Discontinuation of participation in the NIS by the patient has no effect on the patient's routine treatment.

3.3.4.2 *Termination of the NIS by the sponsor*

Following the onset of one or all of the following events, the study can be terminated at the sponsor's discretion:

- Presence of medical or ethical reasons impacting on the continuation of the study in the patients' interests
- Recruitment problems

4 Treatment

4.1 Administered medications

4.1.1 Products

Treatment-naive AF patients will be treated with Pradaxa® hard capsules or VKA in accordance with the Summary of Product Characteristics:

Direct oral thrombin inhibitor:	Pradaxa® 150 mg hard capsules Pradaxa® 110 mg hard capsules
Vitamin K antagonists	e.g. phenprocoumon

Pradaxa® 150 or 110 mg hard capsules contain dabigatran etexilate (active substance: dabigatran).

The choice of VKA is at the discretion of the observing physician. There is no set dosage for these products.

The Summaries of Product Characteristics for Pradaxa® are contained in the NIS study folder in the register "Summaries of Product Characteristics".

For the selected VKA, the observing physician must use the current Summary of Product Characteristics of the product concerned for guidance (www.fachinfo.de).

4.1.2 Allocation of patients and treatment

Each physician must include the first 4 successive eligible AF patients to whom he has decided to prescribe anticoagulant therapy with either dabigatran etexilate or VKA.

Inclusions must be alternated in a ratio of 1 patient on dabigatran etexilate to 1 patient on VKA so as to ensure equal treatment group sizes. The consecutive inclusion of the first 4 eligible AF patients is intended to prevent a selection bias in the choice of patients.

To allow comparability of the patients between the cohorts, matched pairs of dabigatran etexilate and VKA patients are formed for the analysis.

The decision to treat is made irrespective of participation in this NIS and is taken before any consideration of participation.

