2.3 Risk-benefit analysis

Treatment will be administered in accordance with the marketing authorisation of dabigatran etexilate or VKA for AF patients requiring permanent oral anticoagulation.

The medicinal products Pradaxa® or VKA used in this NIS are authorised in the Federal Republic of Germany.

The medicines under observation are not provided by the marketing authorisation holder but are prescribed by the participating physician in accordance with the indication.

The choice of treatment is at the sole discretion of the participating physicians. The NIS has no effect on the patient's treatment. The decision to include a patient in an NIS is distinct from the decision to prescribe the medicinal product.

No additional medical procedures are required other than those which the patient would have received even if they were not included in the NIS. The treatment, including diagnosis and monitoring, follows the standard medical treatment practice.

There is therefore no risk to patients over and above the usual treatment risk for AF patients on anticoagulant therapy with dabigatran etexilate or VKA even outside the NIS.

3 Description of study design and patient population

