3.1.1 Administrative structure of the NIS

About 10,000 potential sites spread over the whole of Germany (general practitioner and primary care internist practices as well as cardiology practices) will be reviewed by members of the Boehringer Ingelheim Pharma GmbH & Co. KG pharmaceutical sales force for their eligibility for participation in the study.

About 3000 sites interested in participating and able to document four patients treated with either dabigatran etexilate or VKA within a period of six months can be selected by Boehringer Ingelheim for possible participation. The 1200 sites that actually participate are chosen by randomisation. It will be assumed that, following the recruitment of about 1200 sites, 1000 sites will actually actively document patients.

Of the 1000 active sites, approximately 2/3 (about 670) will be community-based primary care internists/general practitioners and approximately 1/3 (about 330) community-based cardiologists across Germany.

As a result of the random selection of participants, a high degree of representativeness of the collected data can be obtained and a selection bias in the choice of participating practices can be avoided.

All sites and their employees involved in study participation will be trained before the start of the study in its content and the documentation process.

Following initiation, each doctor should document alternately the first successive eligible patients for whom he has decided to prescribe therapy with dabigatran etexilate or VKA.

The rights and duties of the participating doctors and Boehringer Ingelheim Pharma GmbH & Co. KG derive from the contract concluded on the conduct of an NIS. The participating physicians undertake to conduct the NIS responsibly in accordance with the agreements made in the contract.

Boehringer Ingelheim Pharma GmbH & Co. KG will pay participating physicians compensation in accordance with the listing in the contract concluded with them.

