Rationale for Local Amendment:	
After 6 months of site and patient recruitment it became evident that the targeted patient and site numbers will not be met and that recruitment time should be longer.
 
Therefore the planned patient number will be reduced to 1600 and site number to 800.
 
Recruitment time will be prolonged to 16 months (LPI December 2015), thus study duration will also increase. LPO is now planned for December 2016.
 
Other timelines will change accordingly.
 
New site and patient numbers will be used as calculation basis in the statistical analysis plan.
 
As this amendment is administrative and does not change the content or the nature of this non-interventional study, for readability reasons we refrain from changing every sentence in which site numbers, patient numbers or timelines are mentioned, except for the front page, study synopsis and statistics section.
	
Page 1 of 5		

Proprietary confidential information. © 2015 Boehringer Ingelheim International GmbH or one or more of its affiliated companies. All rights reserved. This document may not - in full or in part - be passed on, reproduced, published or otherwise used without prior written permission.
		

SIGNATURE PAGE(S)

This amendment

- concerns administrative matters only so that the coordinating investigator's signature will not be obtained.
- concerns matters dealing with design elements of the study, in- / exclusion criteria, observations, or safety or efficacy related study elements so that the coordinating investigator's signature needs to be obtained.

Trial Clinical Monitor

May 06 2015
Date

Trial Statistician

Boehringer Ingelheim
Biometrics & Data
Management

Team Member Medicine

Boehringer Ingelheim
Corporate Medical Affairs

Local Clinical Monitor

May 06 2015
Date

Boehringer Ingelheim
Medical Affairs Germany

SIGNATURE PAGE(S)

This amendment

concerns administrative matters only so that the coordinating investigator's signature will not be obtained.

concerns matters dealing with design elements of the study, in- / exclusion criteria, observations, or safety or efficacy related study elements so that the coordinating investigator's signature needs to be obtained.

Trial Clinical Monitor

May 06 2015

Date

Trial Statistician

May 07 2015

Date

Boehringer Ingelheim
Biometrics & Data
Management

Team Member Medicine

Date

Boehringer Ingelheim
Corporate Medical Affairs

Local Clinical Monitor

May 06 2015

Date

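### Protocol 4.1.2 demands both consecutive and strictly alternating inclusion; under independent prescribing at most 12.5% of sites filling 4 places can satisfy both, so the safeguard against patient selection is not delivered as written

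*Protocol*

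**What the plan says.** Protocol 4.1.2 contains two mandatory rules. The first is consecutive inclusion: "Each physician must include the first 4 successive eligible AF patients to whom he has decided to prescribe anticoagulant therapy", with either drug. The second is alternation: "Inclusions must be alternated in a ratio of 1 patient on dabigatran etexilate to 1 patient on VKA", which is there to keep the groups equal in size. The section gives the consecutive rule a purpose of its own: "The consecutive inclusion of the first 4 eligible AF patients is intended to prevent a selection bias in the choice of patients".

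The study does not control the order in which the two drugs are prescribed. Protocol 2.3 states: "The choice of treatment is at the sole discretion of the participating physicians". Protocol 4.1.2 adds: "The decision to treat is made irrespective of participation in this NIS and is taken before any consideration of participation".

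Two other sections word the rule differently. Protocol 3.1.1 merges the two parts: "each doctor should document alternately the first successive eligible patients". Protocol 6 asks for 4 successive patients, alternating 1:1, but only where this is possible. No section says what to do when the next eligible patient is on the drug whose turn it is not.

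Protocol 3.3 has each site list the patients who consented. No record of eligible patients passed over is described.

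Local Amendment 1 changed the scale: "Therefore the planned patient number will be reduced to 1600 and site number to 800". It left the wording of 4.1.2 as it was.

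**The concern.** If a physician's first two eligible patients are both prescribed dabigatran, the physician must either pass over the second, which breaks the consecutive rule, or include both, which breaks alternation. The plan does not say which rule gives way. That leaves room for judgement at the step the consecutive rule was meant to close.

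Consecutive inclusion is the only safeguard the plan names against physicians choosing which patients enter. The random selection in Protocol 3.1.1 concerns practices. The matching concerns comparability between the two cohorts, and SAP 7.4 builds it on four covariates (CHA₂DS₂-VASc, HAS-BLED, age, previous stroke), used as sample size allows. If patients passed over differ from those enrolled in how likely they are to persist, and differently by drug, matching on these four need not remove the difference. With no count of patients passed over, a reader of the report could not tell.

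**Working it through.** The documents give no figure for how many sites can follow both rules, so there is nothing to reproduce first.

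**Inputs**
- Places per physician: 4 (Protocol 4.1.2).
- Average per site: 4000/1000 = 4 as first planned (Protocol synopsis); 1600/800 = 2 after Local Amendment 1.
- Dabigatran share p among a site's eligible new prescriptions: not in the documents. Assumed constant within a site, with successive prescriptions independent. Write q = 1-p. Results are the same for p and 1-p, so p = 0.5, 0.3 and 0.2 also cover 0.7 and 0.8.

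**Formulas**
1. *Both rules met by the first 4 patients.* Only the two alternating sequences qualify, each with probability p²q². The total is 2p²q². For 2 patients it is 2pq. Both are largest at p = 0.5, and averaging over sites with different p cannot exceed that maximum.
2. *Eligible patients seen to fill 4 alternating places.* Starting with dabigatran, the mean is 1 + 2/q + 1/p; starting with VKA it is 1 + 2/p + 1/q. Weighting by p and q gives 3 + 2(p/q + q/p). Subtract 4 for the number passed over.
3. *Enrolled patients are the first two on each drug, under alternation.* Nobody may be skipped before the second or third place. A skip before the fourth place does no harm, because the skipped patient's drug already has its two. The probability is pqp + qpq = pq.
4. *Eligible patients seen to reach 2 per drug in any order.* The mean wait for 2 on one drug is 2/p, and on the other 2/q. The mean of the shorter wait is 2 + 2pq. The mean of the longer wait is therefore 2/p + 2/q - 2 - 2pq = 2/(pq) - 2 - 2pq.

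**Results**

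| | p = 0.5 | p = 0.3 | p = 0.2 |
|---|---|---|---|
| Both rules met, 4 patients | 12.5% | 8.8% | 5.1% |
| Both rules met, 2 patients | 50% | 42% | 32% |
| Alternation: seen to fill 4 places | 7.0 | 8.5 | 11.5 |
| Alternation: passed over | 3.0 | 4.5 | 7.5 |
| Alternation: first two on each drug enrolled | 25% | 21% | 16% |
| First 2 per drug, any order: seen | 5.5 | 7.1 | 10.2 |
| First 2 per drug, any order: passed over | 1.5 | 3.1 | 6.2 |

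**Sensitivity to independence.** Let s be the chance that a prescription differs from the one before. Both rules are then met by 4 patients with probability s³: 12.5% at s = 0.5, 34.3% at 0.7, 72.9% at 0.9.

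**Matched pairs.** Local Amendment 1 plans 0.66 × 800 = 528 pairs, or 2 × 528 = 1056 patients.

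**The case against.** *A workable reading exists.* Protocol 3.1.1 and 6 can be read as: take the next eligible patient on the drug whose turn it is. Applied mechanically, that fixes who is skipped by arrival order and drug, not by prognosis, and so still limits hand-picking. This stands, and for that reason a reader who infers that the plan has no protection at all goes too far. But 4.1.2 does not say this, and the result is not the consecutive series it claims. With 4 places, order within each drug is usually lost too.

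*The probabilities are conditional.* This also stands. They need independent prescriptions and a constant share. If prescriptions tend to alternate, many more sites comply.

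*Physicians may prescribe to fill the open place.* A reader might infer this, since physicians are compensated (Protocol 3.1.1) and Protocol 6 puts the eligibility check after the treatment decision but before the prescription. The documents do not show it. They mention no drug-specific payment, and 2.3, 3.3 and 4.1.2 each separate the decision from inclusion. Nor do they show that physicians put alternation first.

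*Arm comparability is assigned to matching.* True, but matching works on those enrolled; it does not address who was enrolled.

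*The alternative rule also skips patients and can unbalance the arms.* It skips fewer, and those skipped arrive only after their drug's two places are full, so order within each drug is kept. The open drug is still known once one drug is full. On balance: if sites stopped at 2 patients in any order under a fixed total of 1600, the split would be about 480:1120 at p = 0.3 and 320:1280 at p = 0.2, both short of 528 pairs. A cap per arm removes this. For the same arrivals, the alternative never enrols fewer patients in either arm than alternation does.

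*Local Amendment 1 deliberately left number-bearing sentences unedited.* That explains why the figure 4 remains. It does not say which rule governs.

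**Conclusion.** The conflict between the two mandatory rules in Protocol 4.1.2 is real, and 3.1.1 and 6 do not resolve it. Assuming independent prescribing with a constant share at each site, at most 12.5% of sites filling 4 places can meet both. If alternation governs, at most 25% of such sites enrol the first two patients on each drug. The consecutive-inclusion safeguard is therefore not delivered as written at most sites filling 4 places.

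A reader might turn this into a flat statement that at least 87.5% of sites cannot comply. The documents do not support that. The figure is a floor only under the stated assumptions and for 4 patients. At the amended average of 2 per site, the corresponding floor is 50%, and with one patient per drug the order within each drug is intact.

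The size and direction of any bias in persistence are unknown. The calculation counts patients passed over; it does not estimate an effect on the primary endpoint.

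**What to change.** 1. State one governing rule in the same words in Protocol 3.1.1, 4.1.2 and 6. The preferred rule is that each physician documents the first 2 successive eligible patients newly prescribed dabigatran and the first 2 newly prescribed VKA, in whatever order they occur. Close recruitment separately for each arm at the planned 800, to protect balance and the 528 matched pairs.
2. If alternation is kept, say that the next eligible patient on the due drug is taken, and drop the statement that inclusion is consecutive.
3. Under either rule, have each site keep a count, by drug, of eligible patients not enrolled, and report it.
4. State in the report that patients already enrolled under alternation are not a consecutive series. Local Amendment 2 gives 1050 of 1600 enrolled by December 2015, so about 1600 - 1050 = 550 could still have followed a clear rule.

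The cost is revised protocol and site-instruction wording and one tally per site. One arm may also close before the other.

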4.1.3 Dosage

Treatment with dabigatran etexilate or VKA must be given in accordance with the data in the respective Summary of Product Characteristics and is based solely on medical therapeutic needs.

Pradaxa®

The recommended daily dose of Pradaxa® is 300 mg, taken in the form of one 150 mg capsule twice daily. Treatment should be long term.

For the following two patient groups, the recommended daily dose of Pradaxa® is 220 mg, taken as one 110 mg capsule twice daily:

- Patients \geq 80 years

- Patients receiving verapamil concomitantly.

For the following groups, a daily dose of 300 mg or 220 mg of Pradaxa® will be chosen on the basis of an individual assessment of the thromboembolic risk and the bleeding risk:

- Patients between 75 and 80 years old
- Patients with moderate renal impairment
- Patients with gastritis, oesophagitis or gastroesophageal reflux
- Other patients with an increased bleeding risk.

Note: The recommended doses in the Summary of Product Characteristics must not be exceeded.

VKA

VKA have no set dosage.

The dosage of VKA (e.g. phenprocoumon) must be monitored by determining the thromboplastin time and adapted individually. The outcome of this determination is given as INR (International Normalised Ratio).

The target is an effective range of 2.0–3.0 INR.

4.1.4 Other

The medication is supplied on prescription. Patients receive their medicines in the pharmacy. These are commercially available products.

The storage conditions described on the pack apply.

A pill count is not undertaken in connection with the NIS as this cannot be expected in routine care.

4.2 Concomitant medication and restrictions

Patients can receive any medicines they would also receive in their usual routine treatment.

Patients who have the general and special contraindications mentioned in the respective package leaflets or Summaries of Product Characteristics must not be included.

Patients participating at the same time or in the last 30 days in another NIS or interventional clinical trial must not be included.

5 Investigations and observation parameters

Data collection must always be done prospectively.

No data on efficacy in the conventional sense are collected. In this NIS, data on the persistence and adherence to anticoagulant therapy with dabigatran etexilate or VKA will be recorded as target parameters.

5.1 Target parameters

5.1.1 Primary and secondary endpoints

Primary endpoint:

- Proportion of patients still being treated at the time of the 12-month visit with the initially allocated anticoagulant, defined as Kaplan Meier estimate at 12 months for persistence, stratified for dabigatran etexilate and VKA. Persistence is defined as the time between initiation and permanent termination of therapy ⁽²⁰⁾. The start of treatment (documented in the CRF of visit 1) is documented as the start date and the date of discontinuation of treatment with Pradaxa® or VKA as the time of permanent termination of therapy

Secondary endpoints:

- Proportion of patients with low, medium or high adherence at the time of the 6-month visit, stratified for dabigatran etexilate and VKA; categorisation is done on the basis of the Morisky questionnaire.
- Reasons for permanent treatment discontinuation.

